2.4 Study website

The Facebook ads for all treatment groups link to a website built for the study:

<https://www.doctorsforcovidprevention.org>. Treatment 1 participants are directed to a page of video thumbnails with all of the videos recorded by doctors and nurses which answer questions and address myths about the Covid-19 vaccine. Treatments 2 and 3 participants are directed to a website which includes these same videos, and also encourages website visitors to share the vaccine-related content with their friends. The website for treatments 2 and 3 also allows visitors to sign up to be a "vaccine ambassador." Interested website visitors can enroll formally as vaccine ambassadors through our site. They can share their contact information with the study to a) be entered into prize lotteries, b) receive reminders to share content with others, c) be contacted in the future for possible follow-up surveys. These individuals are asked to give their informed consent at this time and are screened based on whether they live in a treated county and whether they are 18 years or older.

The display of doctor/nurse videos on the study website is randomized in two ways. First, website visitors are randomized into two possible video framings: the “myth” site or the “question” site. In the “myth” version, doctors/nurses respond to common myths about the Covid-19 vaccine (e.g. the Covid-19 vaccine can give me Covid), while in the “question” version, the doctors/nurses respond to a question (e.g. can the Covid-19 vaccine give me Covid?). Second, the order that videos are shown is randomized. For the page which only shows video thumbnails, this means the order of the thumbnails is random for each unique website visitor. For the page which encourages people to share vaccine-related content, the random ordering of videos means that the “featured” video is randomized between unique website visitors.

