2.5 Treatment Assignment

The counties in the study sample were randomized into three treatment groups and a control group: 1) a “direct” messaging group (T1), 2) a “friends” messaging group (T2), 3) a “gossips” messaging group (T3), and 4) a control group which did not receive any Facebook ads from us.

Randomization was conducted at the county level. County-level randomization was stratified by three characteristics: 1) state, 2) political leaning (according to 2020 election results), and 3) baseline vaccination rates. For political leaning, counties were divided into below- and above- median GOP vote in the 2020 presidential election. For baseline vaccination rates, counties were divided into above- and below-median percentage of the population that had received the 1st dose of Covid-19 vaccine.

After stratifying on these three variables, strata were adjusted so that no stratum was smaller than 9 counties. Strata with fewer than nine counties were dissolved by baseline percentage of population with first dose of vaccine. For the three states (South Carolina, Michigan, and Wyoming) where this does not result in strata that have at least nine counties, we dissolve instead by baseline GOP vote share. In total, this left us with 47 strata.

Exceptions: County-level GOP votes were not available for Alaska, and so this stratification variable was used for the other 18 states in the sample only.

Out of the 1,397 counties which fit the eligibility criteria for the experiment, we assigned 468 counties to the control group, 310 counties to T1 (“direct” messaging) treatment, 309 counties to T2 (“friends” messaging), and 310 counties to T3 (“gossips” messaging).

3. Hypotheses

Primary hypotheses:

1. Do the ads affect the new Covid-19 vaccinations in treated areas?
 - 1st dose of vaccine
 - 2nd dose/completed vaccination
 - Booster shots
2. Which type of messaging (“direct,” “friends,” or “gossips”) is most effective at driving engagement and shares of vaccine-related content, as well as new vaccinations?

3. Is myth- or question-based messaging more effective at eliciting engagement with vaccine-related content?

Secondary hypotheses:

4. Do the ads affect Covid-19 cases, hospitalizations, or symptoms in treated areas?
5. Do the ads spill over onto other areas that are connected to the treatment counties?
 - Behavioral spillovers: new vaccinations
 - Covid-19 case, hospitalization, symptom impacts

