4.4 Regression Analysis

1. Effects of treatment on county-level outcomes (Covid-19 vaccinations, content engagement, other behavioral or survey outcomes):

- (a) Main analysis: $Y_{ct} = \alpha_t + \gamma_c + \beta_1 Direct_{ct} + \beta_2 Friends_{ct} + \beta_3 Gossips_{ct} + \delta Y_{c0} + \epsilon_{ct}$
 - Y_{c0} is a baseline measure of the outcome
 - *Direct, Friends* and *Gossips* are the three treatment groups. Treatment is assigned at the county level. We may also pool together friends and gossips, or all three treatment groups in some specifications.
- (b) Heterogeneous effects of treatment: $Y_{ct} = \alpha_t + \gamma_c + \beta_1 X_{ct} + \beta_2 Treat_{ct} + \beta_3 Treat_{ct}X_{ct} + \epsilon_{ct}$
 - We plan to explore heterogeneity along the following dimensions:
 - Political leaning (red/blue) – this was a stratification variable
 - Baseline vaccination rates – we stratified on baseline population percentage with 1st dose of vaccine
 - Percentage white/non-white
 - Relevant vaccine mandates
 - Prior/baseline infection rates
 - Urban vs rural

We may look at heterogeneity in specifications which consider each treatment group separately, as well as specifications which pool together treatment groups.

- (c) Distributional impacts using quantile regression
 - We may repeat the exercises above with quantile regressions.
- (d) Do people who visit the study website from different treatment groups click on different content (e.g. vaccine-related videos)? For example, do website visitors respond to myth vs fact videos differentially by treatment group?

2. Comparing the efficacy of myth- vs question-based messaging

- (a) $Y_{ict} = \alpha_t + \gamma_c + \beta \mathbb{1}(Myth_{ict}) + \epsilon_{ict}$
 - Y_{ict} stands for engagement-related outcomes such as video views, website visits, and video shares
 - We will examine myth- vs question-based messaging at both the Facebook ad level and at the website level. (The videos vary in whether they are myth- or question-based both in the Facebook ads which are served to users, as well as in the videos which are visible to website visitors.)

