4.7 Inference

For our core analyses, we will use heteroskedasticity-robust standard errors. We will check for additional statistical robustness following the approaches outlined in Section 5 of the Supplementary Appendix of [this paper](#).

5. Funding and Human Subjects Review

Facebook is supplying sufficient ad credits to fund the campaign. The IRB at MIT is serving as the primary institution of record and has entered into a reliance agreement with Harvard, Stanford, Massachusetts General Hospital, and Yale.

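### At the Facebook ad level, model 2(a) tests myth versus question framing with errors that ignore what all rows of one video share, so a primary hypothesis may get standard errors that are too small

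*Combined protocol and SAP*

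**What the plan says.** Section 3 lists the framing question as primary hypothesis 3: "Is myth- or question-based messaging more effective at eliciting engagement with vaccine-related content". Section 4.4, item 2(a) answers it by regressing engagement on a myth indicator with a time effect and a county effect. The outcome is described only by example: "Y_{ict} stands for engagement-related outcomes such as video views, website visits, and video shares". The index i is not defined. The same equation serves the ads and the website: "We will examine myth- vs question-based messaging at both the Facebook ad level and at the website level". For the ads, the plan says what carries the framing: "The videos vary in whether they are myth- or question-based both in the Facebook ads which are served to users".

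Section 4.7 sets the inference: "For our core analyses, we will use heteroskedasticity-robust standard errors". The next sentence adds a check by reference to an outside paper: "We will check for additional statistical robustness following the approaches outlined in Section 5 of the Supplementary Appendix of". No clustering, video term, topic term or randomization test is named in the plan itself.

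Section 2.4 describes how framing is assigned on the website: "website visitors are randomized into two possible video framings". No corresponding statement is made for the ads.

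**The concern.** Within one ad video the myth indicator does not vary. Every row from that video, in whatever county and on whatever date, shares its speaker, topic, wording and editing. Some videos will draw more engagement than others for those reasons alone. County and time effects do not absorb a component that belongs to the video. Heteroskedasticity-robust errors allow for unequal variances but still treat rows as uncorrelated.

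Clustering by county would not help, because the shared component runs across counties. In a balanced panel the video effects left in the residuals sum to zero within each framing in every county, so a county-clustered variance does not see them.

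If rows are repeated, further rows from the same video add little information on whether framing in general matters. The risk is that a difference between particular clips is reported, with too narrow an interval, as a difference between myth- and question-based messaging. Since this is a primary hypothesis, it is reasonable to read it as one of the core analyses to which Section 4.7 applies.

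**Working it through.** **Counts from the plan.** Section 2.1: 468 + 310 + 309 + 310 = 1,397, and 1,402 − 5 = 1,397, so the county count reproduces. Ads run in 310 + 309 + 310 = 929 treated counties. Section 2.2 mentions questions and myths only for the direct-messaging ads, so 310 counties is the low case and 929 the high case. Section 2.3 gives five weeks, December 22, 2021 to January 27, 2022, which is 36 days by subtraction. The plan gives no sample size, power or number of videos for this comparison.

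**Assumptions.** One row per video, county and period; balanced delivery; no true framing effect; two-sided 5% test; video-level ICC from 0.0001 to 0.05; 3 to 20 videos per framing.

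**Formula.** With m rows per video, the true variance of the framing contrast is DEFF = 1 + (m − 1) × ICC times the row-level variance. The actual false-positive rate is 2 × [1 − Φ(1.96/√DEFF)].

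**Example.** For 310 counties × 5 weeks, m = 1,550. At ICC 0.01, DEFF = 1 + 1,549 × 0.01 = 16.49, 1.96/√16.49 = 0.483, and the rate is 63%.

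| Rows per video (m) | ICC 0.0001 | ICC 0.001 | ICC 0.01 | ICC 0.05 |
|---|---|---|---|---|
| 310 × 5 = 1,550 | 7% | 22% | 63% | 82% |
| 929 × 5 = 4,645 | 11% | 41% | 78% | 90% |
| 310 × 36 = 11,160 | 18% | 57% | 85% | 93% |
| 929 × 36 = 33,444 | 35% | 74% | 92% | 96% |

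**Fewer rows per video, same formula.**
- ICC 0.001: 5.2% at 20 rows, 6.2% at 100, 8.7% at 310.
- ICC 0.01: 7.2% at 20 rows.
- ICC 0.05: 16% at 20 rows, 42% at 100, 63% at 310.

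**Simulation check.** Balanced panel, 310 counties × 5 weeks, county and week effects removed, 1,000 runs per setting, 3, 5, 10 or 20 videos per framing. The row-level robust test rejected in 4-5% of runs at ICC 0, 18-24% at 0.001, 61-66% at 0.01 and 81-84% at 0.05. The number of videos made little difference. A t-test on video means rejected in 3.7-6.6% of runs across all settings. The Monte Carlo standard error at 5% is √(0.05 × 0.95/1,000) = 0.7 percentage points.

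**If half the between-video variance is shared within a topic.** A separate simulation (5, 10 or 20 myth/question pairs, same panel) gave about 15%, 49-52% and 75-77% for the robust test at ICC 0.001, 0.01 and 0.05. County-clustered errors gave about the same: 15%, 48-52% and 75-78%. A paired test on topic-level differences gave 3.5-6.5%.

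**Degrees of freedom after the fix.** With 3, 5, 10 or 20 videos per framing, df = 4, 8, 18 or 38 and the critical t is 2.78, 2.31, 2.10 or 2.02.

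**Sign-flip test on pairs.** The smallest two-sided p-value with n pairs is 2/2ⁿ: 2/32 = 0.0625 for five and 2/64 = 0.031 for six.

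**The case against.** **The row structure is not stated.** This is the strongest objection, and it stands. Because i is undefined, repeated rows per video are a reading of the subscripts and the county effect. With one row per video the problem would not arise, and with few rows and a low ICC the inflation is slight. The claim is therefore conditional.

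**The outside appendix may contain a suitable method.** It may, but its content is not in the documents, and Section 4.7 offers it as an additional check, not as the main inference.

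**Section 4.6 adds machine-selected controls to every regression.** The list is open-ended, so the printed equation is not the whole model. The named candidates are county- or state-level, and none is a video or topic term. A full set of video indicators could not be added, because it would absorb the myth indicator. Topic or speaker controls might shrink the shared component, but would not by themselves make row-level errors valid.

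**The target may be the deployed clips only.** This is a legitimate estimand. If framing was randomized at exposure, row-level errors could be valid for the contrast between those particular clips. The plan states neither that target nor that randomization for the ads, and hypothesis 3 is worded about messaging in general.

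A reader might also infer three things that the documents do not support:
- That there are only a few ad videos. Section 2.2 mentions a set without giving its size, and the inflation depends on rows per video and ICC, hardly on the number of videos.
- That the ads come in matched topic pairs. The matched example, in which "doctors/nurses respond to a question (e.g. can the Covid-19 vaccine give me Covid" and the myth version covers the same topic, is in Section 2.4 and describes the website.
- That the website comparison has the same fault. There, framing is randomized by visitor, and the plan describes no layout with repeated rows per visitor for this model.

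**Conclusion.** The point holds in conditional form. The plan places framing at the level of the ad video, gives model 2(a) no term for the video, and names an error estimator that assumes uncorrelated rows. If rows repeat within videos, the stated inference for a general framing effect can be too optimistic.

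On the assumptions above, the actual error rate of a nominal 5% test runs from about 5-7% (20 rows per video at ICC 0.001 or 0.01, or 1,550 rows at ICC 0.0001) through about 22% and 63% to about 82% (1,550 rows at ICC 0.001, 0.01 and 0.05). Layouts with more rows are worse at each ICC. None of the ICC, the rows per video or the number of videos is in the plan, so this is a range of possibilities, not an estimate.

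It would be too strong to say that the analysis will declare a framing effect. The documents support only that the stated errors do not protect against a false one. The correction should be made, because it replaces the stated rule for a primary hypothesis with one that keeps its level whatever the ICC.

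**What to change.** In Section 4.4, item 2 and Section 4.7, for the Facebook ad-level comparison:

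1. Define i and the row layout, and state how framing was assigned to ads.
2. Replace row-level robust errors with errors clustered by video and a small-cluster correction, or use a t-test on video means. Report the number of videos per framing beside the estimate.
3. Where ad videos do exist as matched myth and question versions of one topic, add topic effects and cluster by topic with the same correction, or use a paired t-test on topic-level differences. Use a sign-flip test only with at least six pairs, since with five it cannot reach 5%.
4. If the target is only the set of clips that was deployed, say so and limit the conclusion to those clips.

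The cost is plan wording and a different error option; the only data requirement is a video identifier on each ad-level row. The downside is wider intervals, and low power if there are few videos: with three per framing the critical t is 2.78 on 4 df.

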4.5 Spillovers and Networks Analysis

We may use Facebook network information (SCI) at the zip code level to study the dynamics of information sharing about Covid-19 vaccination.

4.6 Controls

For all regressions, we will use machine learning techniques to select the controls. Potential controls include: baseline Covid-19 vaccination or case rates, state fixed effects, county-level demographic information from the census, county- or state-level vaccination policies, and many other attributes.

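### Counties were randomised within 47 strata, but no regression commits to stratum or stratum-by-period terms; forcing them in is nearly free and recovers whatever precision the strata carry

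*Combined protocol and SAP*

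**What the plan says.** Section 2.5 (Treatment Assignment) reports that "County-level randomization was stratified by three characteristics": state, 2020 GOP vote above or below the median, and baseline first-dose rate above or below the median. Small cells were merged: "strata were adjusted so that no stratum was smaller than 9 counties". The result: "In total, this left us with 47 strata". The allocation was 468 control, 310 T1, 309 T2 and 310 T3.

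Section 4.4 (Regression Analysis) writes the main model with period effects, a term indexed by county (gamma_c, not defined), three arm indicators and Y_c0, which "is a baseline measure of the outcome". The stratifiers appear only in the list of heterogeneity dimensions, where the plan notes of political leaning that "this was a stratification variable" and of baseline rates that "we stratified on baseline population percentage with 1st dose of vaccine".

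Section 4.6 (Controls) says: "For all regressions, we will use machine learning techniques to select the controls". The candidates closest to the design are listed as possibilities: "Potential controls include: baseline Covid-19 vaccination or case rates, state fixed effects". Neither the strata nor GOP vote is named.

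Section 4.7 (Inference) specifies heteroskedasticity-robust standard errors and refers further checks to an external appendix.

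**The concern.** The randomisation and the analysis are not connected. Blocking on strata removes between-stratum differences from the treatment contrast. If the model has no stratum terms, those differences stay in the residual, so the standard error describes a less precise experiment than the one run. Confidence intervals are too wide, tests are conservative, and power built into the design goes unused.

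Which terms are missing depends on the data layout, which the plan leaves open:

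- **gamma_c is a full set of county effects.** It already absorbs stratum levels. What stays in the error is stratum-specific change over the campaign, so stratum-by-period terms are the ones that matter. Y_c0 is then collinear with gamma_c.
- **Only post-launch data are used.** County effects are collinear with treatment and must be dropped. Beyond Y_c0, nothing then guarantees stratum adjustment.

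As things stand, an unspecified selection algorithm decides whether the primary model reflects the randomisation.

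**Working it through.** **Inputs from the plan.** 1,402 − 5 = 1,397 counties (section 2.1), and 468 + 310 + 309 + 310 = 1,397, so the stated total reproduces. There are 47 strata in 19 states. The plan gives no alpha, effect size, SD or power; two-sided 5% and 80% power are assumed.

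**Allocation.** A 3:2:2:2 split of 1,397 would be 465.7/310.4/310.4/310.4, close to the stated totals. This is consistent with one ratio throughout, but overall totals cannot prove it stratum by stratum.

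**What state effects could cover.** The merging described in section 2.5 is read as within state, so strata nest in states. There are 47 − 1 = 46 stratum contrasts. State effects span 19 − 1 = 18, which leaves 28 within-state contrasts even if every state effect is selected. A selected baseline rate, or Y_c0, may pick up part of these.

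**Cost.** With one row per county, residual degrees of freedom fall from 1,397 − 4 = 1,393 to 1,393 − 46 = 1,347, and the t critical value moves from 1.96167 to 1.96173.

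**Gain.** Let R be the share of residual variance that strata explain after everything else in the model, and k = √(1 − R). For one arm against control, the standard error in residual-SD units is √(1/468 + 1/310) = 0.0732. The effect with 80% power on that standard error is (1.960 + 0.842) × 0.0732 = 0.205 SD. Write d = 1.960 + 0.842 = 2.802. Then:

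- excess in the reported SE without stratum terms = 1/k − 1
- true type I error without them = 2[1 − Φ(1.960/k)]
- power without them = Φ((d − 1.960)/k)
- power with them = Φ(d/k − 1.960)

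Example, R = 20%: k = 0.894; 1/k − 1 = 11.8%; power is Φ(0.842/0.894) = 82.7% without and Φ(2.802/0.894 − 1.960) = 87.9% with.

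| R (assumed) | SE too large by | True type I error | Power without | Power with | Gain (points) |
|---|---|---|---|---|---|
| 0% | 0% | 5.0% | 80.0% | 80.0% | 0 |
| 2% | 1.0% | 4.8% | 80.2% | 80.8% | 0.5 |
| 5% | 2.6% | 4.4% | 80.6% | 82.0% | 1.4 |
| 10% | 5.4% | 3.9% | 81.2% | 84.0% | 2.7 |
| 20% | 11.8% | 2.8% | 82.7% | 87.9% | 5.3 |
| 30% | 19.5% | 1.9% | 84.3% | 91.8% | 7.5 |

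**Simulation check.** This used 10,000 trials with one change per county, 1,397 counties, 47 uneven strata of 9 to 100, blocked 3:2:2:2 assignment and HC1 standard errors. At R = 0/5/10/20/30%:

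- Type I error was 5.0/4.3/3.7/2.9/2.0% without stratum terms, and 4.9% with them at every R.
- Power was 80.2/80.8/81.3/82.6/84.1% without and 80.2/82.0/84.0/87.8/92.0% with.

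**Longer panel.** With four pre and five post periods (assumed), R = 20%, county effects and AR(1) errors at rho 0/0.5/0.9 (1,500 runs each), unclustered robust standard errors gave type I error of 5.1/17.1/26.0% without stratum-by-period terms and 5.3/18.6/28.7% with them. Clustering by county gave 3.3/2.7/2.5% without and 5.6/5.1/5.1% with. The pattern in the table therefore returns only once serial correlation is dealt with.

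**The case against.** The strongest reply is that the benefit is not demonstrated. R is unknown. The plan writes a county term and Y_c0 into the main model and lists state effects and baseline rates as candidates. The candidate list is open-ended, and selection tends to keep variables that predict the outcome. If that works well, R is small, and at R up to 10% the gain is at most 2.7 points. That stands, and it is why the size is given as a range that includes zero. It does not remove the point, because a candidate control is not a commitment, and county effects do not remove stratum-specific change.

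Second, the equation reads most naturally as a panel, while the table assumes one row or one change per county. This also stands as a limit. In a longer panel with unclustered standard errors, tests over-reject with or without stratum terms. That is a separate problem, which stratum terms do not cure.

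Third, the appendix cited in section 4.7 may contain inference that respects the stratified draw. It cannot be seen here, and the plan presents it as an additional check rather than the core analysis.

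Finally, the omission makes tests conservative in the layout where the figures apply, so it creates no false positives there. That limits the weight of the point. It does not argue against a change that costs almost nothing.

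**Conclusion.** The concern holds for the county-level treatment regressions: the design strata are not carried into the analysis. It should be corrected, but it is a matter of efficiency, not validity. With one row or one pre/post change per county and similar allocation ratios across strata, there is no bias. Reported standard errors are 0 to 19.5% too large and 0 to 7.5 points of power are forgone for R between 0 and 30%. R is an assumption throughout. It will be near the low end if strata differ mainly in level and county effects or Y_c0 are kept, or if selection picks up state effects and baseline rates. The website comparison of myth and question framing is randomised by visitor, so county strata matter little there.

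**What to change.** In section 4.4, state the data layout of the primary model and add the matching sentence:

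- Post-period or change model: *Fixed effects for the 47 randomisation strata and Y_c0 are included; gamma_c is omitted.*
- Pre/post panel: *gamma_c are county effects; stratum-by-period effects for the 47 strata are included; Y_c0 is omitted as collinear.*

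If more than two periods are analysed, the panel sentence still applies, but the serial-correlation problem in section 4.7 must be settled as well, for example by clustering on county.

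In section 4.6, add: *These terms are forced in. Machine learning chooses only additional pre-launch controls.*

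In section 2.5, state the allocation ratio used within strata, so that readers can verify the no-bias condition.

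The cost is plan wording and 46 degrees of freedom; the strata were already formed for the randomisation. At R = 0, simulated power is 80.2% with or without the terms.
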